#### **8.8.4. Electrocardiogram**

The statistical analysis of ECG data will be performed by [REDACTED] and is not covered in the current statistical analysis plan. A separate statistical analysis plan will be prepared by [REDACTED] for these analyses.

#### **8.8.5. Other safety endpoints**

Descriptive analyses will be provided by cohorts, subgroups and overall on the mITT.

## 8.9. Analysis of other endpoints and variables

Analyses of other endpoints will be performed on the mITT. Results will be displayed by cohorts, subgroups and overall.

### 8.9.1. Vital signs

Descriptive statistics will be provided by visit.

### 8.9.2. Clinical signs and symptoms of HAT

Descriptive statistics will be provided by visit.

### 8.9.3. Physical examination

Descriptive statistics will be provided by visit.

### 8.9.4. Neurological examination

Descriptive statistics will be provided by visit.

### 8.9.5. HAT diagnosis (i.e. examination of blood, lymph and CSF samples)

Descriptive statistics will be provided by visit.

### 8.9.6. Pharmacokinetics

The statistical analysis will be performed by [REDACTED] and will be described in a separate statistical analysis plan.

### 8.9.7. Electrocardiogram

The statistical analysis will be performed by [REDACTED] and will be described in a separate statistical analysis plan.

## 8.10. Interim analyses

No interim analysis is planned. This a change from the analysis planned in the protocol (cf. [Section 11](#) for further details).

## 8.11. Unscheduled visit

During the data review, any efficacy and safety data from unscheduled visit which must be taken into account in the analysis will be identified.

Other data from unscheduled visits will only be tabulated in listings except for time to event analyses where they will be taken into account.

## 8.12. Data and Safety Monitoring Board (DSMB)

A DSMB, composed of at least 3 members independent of the Investigators and the Sponsor, will be set up prior to the start of the study. The DSMB will monitor the study in order to minimize any risk of harm to the patients included in the study.

At each of its meetings, the DSMB will examine safety data and all information related to SAEs, and will issue recommendations regarding the study if the benefit-to-risk ratio for patients seems to be in jeopardy. The data and the intervals for review will be decided before, or shortly after the start of the study and will be recorded in the DSMB Charter.

DNDI-FEX-09-HAT (DNDI)	Statistical Analysis Plan Version 3.0 – 30/09/2022	Page 22 / 37
------------------------	---	--------------

The organization of the DSMB will be described in the DSMB Charter, which will be prepared and approved prior to the first planned futility analysis.

Additional *ad hoc* members may be invited to join the DSMB if any safety concerns emerge, in order to give additional support to the competencies already present.

DNDi-FEX-09-HAT (DNDi)	Statistical Analysis Plan Version 3.0 – 30/09/2022	Page 23 / 37
------------------------	---	--------------

## 9. DISPLAY TEMPLATES

### 9.1. List of Tables, Figures and Listings

#### **1. TRIAL PATIENTS:**

##### **1.1 Disposition of patients**

Statistical Table 1.1.1: Disposition of patients

##### **1.2 Important protocol deviations**

Statistical Table 1.2.1: Protocol deviations (ITT)

##### **1.3 Analysis sets**

Statistical Table 1.3.1: Analysis datasets

##### **1.4 Demographic data and baseline characteristics**

Statistical Table 1.4.1: Demographic data (mITT)

Statistical Table 1.4.2: Vital signs at baseline (mITT)

Statistical Table 1.4.3: Clinical signs and symptoms of HAT at baseline (mITT)

Statistical Table 1.4.4: Physical examination at baseline (mITT)

Statistical Table 1.4.5: Neurological examination at baseline (mITT)

Statistical Table 1.4.6: HAT diagnosis (examination of blood, lymph and CSF samples) at screening (mITT)

##### **1.5 Medical history**

Statistical Table 1.5.1: Medical history (mITT)

##### **1.6 Prior and concomitant therapies**

Statistical Table 1.6.1: Prior therapies (mITT)

Statistical Table 1.6.2: Concomitant treatments (mITT)

##### **1.7 Extent of exposure**

Statistical Table 1.7.1: Extent of exposure (mITT)

#### **2. Primary and secondary endpoints**

##### **2.1 Primary efficacy endpoint**

###### **2.1.1 Primary analysis**

Statistical Table 2.1.1.1: Success rate at 18 months (mITT - overall)

###### **2.1.2 Sensitivity analyses**

Statistical Table 2.1.2.1: Success rate at 18 months (PP - overall)

Statistical Table 2.1.2.2: Success rate at 18 months (Evaluable set - overall)

###### **2.1.3 Secondary analyses**

Statistical Table 2.1.3.1: Success rate at 18 months by cohorts and subgroups (mITT)

## **2.2 Secondary endpoints**

### **2.2.1 Endpoint at 12 months**

Same outputs as in Section 2.1.

### **2.2.2 Analysis of failures**

Statistical Table 2.2.2.1: Logistic regression: Model 1 – all patients (mITT)

Statistical Table 2.2.2.2: Logistic regression: Model 2 – all patients (mITT)

Statistical Table 2.2.2.3: Logistic regression: Model 3 – all patients (mITT)

Statistical Table 2.2.2.4: Logistic regression: Model 4 – all patients (mITT)

Statistical Table 2.2.2.5: Logistic regression: Model 5 – all patients (mITT)

### **2.2.3 Compliance**

Statistical Table 2.2.3.1: Compliance – outpatients (ITT)

Statistical Table 2.2.3.2: Compliance – all patients (ITT)

### **2.2.4 Feasibility**

Statistical Table 2.2.4.1: Feasibility – outpatients (ITT)

### **2.2.5 Packaging**

Statistical Table 2.2.5.1: Packaging – outpatients (ITT)

## **3. Safety**

### **3.1 Adverse events**

Statistical Table 3.1.1: Overall summary of AEs (mITT)

Statistical Table 3.1.2: TEAE by SOC and PT (mITT)

Statistical Table 3.1.4: Drug-related TEAE by SOC and PT (mITT)

Statistical Table 3.1.5: Serious TEAE by SOC and PT (mITT)

Statistical Table 3.1.7: Serious drug-related TEAE by SOC and PT (mITT)

### **3.2 Laboratory examinations**

#### **3.2.1 Haematology:**

Statistical Table 3.2.1.1: Descriptive analysis of haematology parameters at baseline, at each time points and changes from baseline at each time points (mITT)

Statistical Figure 3.2.1.2: Changes over time of each haematology parameters (mITT)

Statistical Table 3.2.1.3: Shift tables between baseline and each time points of haematology parameters' severity (mITT)

Statistical Table 3.2.1.4: Shift tables of CTCAE grades between baseline and each time points of haematology parameters (mITT)

Statistical Figure 3.2.1.5: Scattergrams between baseline value and value at each time points of each haematology parameters (mITT)

### **3.2.2 Biochemistry:**

Same outputs as above (except Figure 3.2.1.2).

Statistical Table 3.2.1.6: Liver function tests (mITT)

### **3.2.3 Urinalysis:**

Statistical Table 3.2.3.1: Shift tables between baseline and each time points of urinalysis parameters (mITT)

## **4. Other endpoints**

Statistical Table 4.1: Descriptive analysis of vital signs by visit (mITT)

Statistical Table 4.2: Descriptive analysis of clinical signs and symptoms of HAT by visit (mITT)

Statistical Table 4.3: Descriptive analysis of physical examination by visit (mITT)

Statistical Table 4.4: Descriptive analysis of neurological examination by visit (mITT)

Statistical Table 4.5: Descriptive analysis of HAT diagnosis (examination of blood, lymph and CSF samples) by visit (mITT)

## **5. Individual data listings:**

The following listings will be included in the clinical study report. They will include all patients included in the study and all visit information will be presented chronologically (including unscheduled visits).

### **5.1 Discontinued patients**

- Disposition of patients – all patients
- Study discontinuation – all patients

### **5.2 Protocol deviations**

- Informed consent
- Inclusion/Exclusion criteria
- Eligibility
- Protocol deviation

### **5.3 Patients excluded from the efficacy analysis**

- Patients excluded from ITT
- Patients excluded from Treated set
- Patients excluded from PPS

### **5.4 Demographic data**

- Patients characteristics
- Diagnosis-parasite in blood and/or lymph
- Lumbar puncture (parasite and WBC)

### **5.5 Medical history, prior and concomitant therapies**

- Medical history
- Pre-treatment of helminthiasis

DNDi-FEX-09-HAT (DNDi)	Statistical Analysis Plan Version 3.0 – 30/09/2022	Page 26 / 37
------------------------	---	--------------

- Pre-treatment of malaria
- Prior medications
- Concomitant treatments

#### **5.6 Compliance and/or drug concentration data**

- Treatment administration
- Compliance

#### **5.7 Individual efficacy response data**

- Diagnosis-parasite in blood and/or lymph
- Lumbar puncture (parasite and WBC in CSF)
- Efficacy outcomes at 18 and 12 months
- Listing of failures

#### **5.8 Adverse event listings**

- All Adverse Events
- Serious Adverse Events
- TEAE leading to permanent or temporary treatment discontinuation
- Drug-related TEAE which occurred during the treatment period

#### **5.9 Individual laboratory measurements**

- Haematology
- Biochemistry
- Thyroid function
- Patients with clinically significant abnormalities in laboratory parameters

#### **5.10 Other endpoints**

- Vital Signs
- Clinical signs and symptoms of HAT
- Physical examination
- Neurological examination
- HAT diagnosis (examination of blood, lymph and CSF samples)

## 9.2. Display templates

The display templates in this section are designed for 4 groups. They will be adapted to display 2 groups or 3 groups, when specified in [Section 8](#).

### 9.2.1. Disposition of patients

Disposition of patients	Inpatients (N=XX)	Outpatients (N=XX)	Stage 1 and Intermediate (N=XX)	Stage 2 (N=XX)	Total (N=XX)
Screened positive (=informed consent signed)	xxx	xxx	xxx	xxx	xxx
- Visit Day 0 (for outpatients) or Day 1 (for inpatients) performed?	xx (xx.x%)	xx (xx.x%)	xx (xx.x%)	xx (xx.x%)	xx (xx.x%)
Included (=all in/ex criteria respected)	xxx	xxx	xxx	xxx	xxx
Treated	xxx	xxx	xxx	xxx	xxx
- Study completed according to protocol	xx (xx.x%)	xx (xx.x%)	xx (xx.x%)	xx (xx.x%)	xx (xx.x%)
- Premature withdrawal:	xx (xx.x%)	xx (xx.x%)	xx (xx.x%)	xx (xx.x%)	xx (xx.x%)
- Death	xx (xx.x%)	xx (xx.x%)	xx (xx.x%)	xx (xx.x%)	xx (xx.x%)
- Lost to follow-up	xx (xx.x%)	xx (xx.x%)	xx (xx.x%)	xx (xx.x%)	xx (xx.x%)
- Withdrawal of consent	xx (xx.x%)	xx (xx.x%)	xx (xx.x%)	xx (xx.x%)	xx (xx.x%)
- Investigator's decision	xx (xx.x%)	xx (xx.x%)	xx (xx.x%)	xx (xx.x%)	xx (xx.x%)
- Adverse event (AE)	xx (xx.x%)	xx (xx.x%)	xx (xx.x%)	xx (xx.x%)	xx (xx.x%)
- Rescue treat. prescribed < D11 (1)	NA	xx (xx.x%)	xx (xx.x%)	xx (xx.x%)	xx (xx.x%)
- Rescue treat. due to relapse	xx (xx.x%)	xx (xx.x%)	xx (xx.x%)	xx (xx.x%)	xx (xx.x%)
- Other reason	xx (xx.x%)	xx (xx.x%)	xx (xx.x%)	xx (xx.x%)	xx (xx.x%)
- Treatment completers (2)	xx (xx.x%)	xx (xx.x%)	xx (xx.x%)	xx (xx.x%)	xx (xx.x%)
- Death not related to the IP or HAT	xx (xx.x%)	xx (xx.x%)	xx (xx.x%)	xx (xx.x%)	xx (xx.x%)
- Minor PV	xx (xx.x%)	xx (xx.x%)	xx (xx.x%)	xx (xx.x%)	xx (xx.x%)
- Major PV	xx (xx.x%)	xx (xx.x%)	xx (xx.x%)	xx (xx.x%)	xx (xx.x%)
- Lumbar puncture performed at EoH	xx (xx.x%)	xx (xx.x%)	xx (xx.x%)	xx (xx.x%)	xx (xx.x%)
- Lumbar puncture performed at M3	xx (xx.x%)	xx (xx.x%)	xx (xx.x%)	xx (xx.x%)	xx (xx.x%)
- (...)	xx (xx.x%)	xx (xx.x%)	xx (xx.x%)	xx (xx.x%)	xx (xx.x%)
- Attended visit D1	xx (xx.x%)	NA	xx (xx.x%)	xx (xx.x%)	xx (xx.x%)
- Attended visit (...)	(...)	NA	(...)	(...)	(...)
- Attended visit D10	xx (xx.x%)	NA	xx (xx.x%)	xx (xx.x%)	xx (xx.x%)
- Attended visit EoT	xx (xx.x%)	xx (xx.x%)	xx (xx.x%)	xx (xx.x%)	xx (xx.x%)
- Attended visit EoH	xx (xx.x%)	NA	xx (xx.x%)	xx (xx.x%)	xx (xx.x%)
- (...)	xx (xx.x%)	xx (xx.x%)	xx (xx.x%)	xx (xx.x%)	xx (xx.x%)
- Attended visit M18	xx (xx.x%)	xx (xx.x%)	xx (xx.x%)	xx (xx.x%)	xx (xx.x%)
First patient screened					dd-mmm-yy
First study-drug admin. of the first patient					dd-mmm-yy
First study-drug admin. of the last patient					dd-mmm-yy
Last patient last visit					dd-mmm-yy
Study duration (days)					xxx

(1) Rescue treatment prescribed for outpatients before Day 11.

(2) Patients who received all of the protocol-planned doses.

## 9.2.2. Protocol deviations

Protocol Deviations		Inpatients (N=XX)		Outpatients (N=XX)		Stage 1 and Intermediate (N=XXX)		Stage 2 (N=XXX)		Total (N=XXX)	
		n Patients	nDeviations	n Patients	nDeviations	n Patients	nDeviations	n Patients	nDeviations	n Patients	nDeviations
Major protocol deviation	Yes	n (xx.x%)	xx	n (xx.x%)	xx	n (xx.x%)	xx	n (xx.x%)	xx	n (xx.x%)	xx
Type of major protocol deviation	Type 1	n (xx.x%)	xx	n (xx.x%)	xx	n (xx.x%)	xx	n (xx.x%)	xx	n (xx.x%)	xx
	Type 2	n (xx.x%)	xx	n (xx.x%)	xx	n (xx.x%)	xx	n (xx.x%)	xx	n (xx.x%)	xx
	Type ...	n (xx.x%)	xx	n (xx.x%)	xx	n (xx.x%)	xx	n (xx.x%)	xx	n (xx.x%)	xx
	Type n	n (xx.x%)	xx	n (xx.x%)	xx	n (xx.x%)	xx	n (xx.x%)	xx	n (xx.x%)	xx
Minor protocol deviation	Yes	n (xx.x%)	xx	n (xx.x%)	xx	n (xx.x%)	xx	n (xx.x%)	xx	n (xx.x%)	xx
Type of minor protocol deviation	Type 1	n (xx.x%)	xx	n (xx.x%)	xx	n (xx.x%)	xx	n (xx.x%)	xx	n (xx.x%)	xx
	Type 2	n (xx.x%)	xx	n (xx.x%)	xx	n (xx.x%)	xx	n (xx.x%)	xx	n (xx.x%)	xx
	Type ...	n (xx.x%)	xx	n (xx.x%)	xx	n (xx.x%)	xx	n (xx.x%)	xx	n (xx.x%)	xx
	Type n	n (xx.x%)	xx	n (xx.x%)	xx	n (xx.x%)	xx	n (xx.x%)	xx	n (xx.x%)	xx

### 9.2.3. Analysis datasets

Analysis datasets	Inpatients (N=XX)	Outpatients (N=XX)	Stage 1 and Intermediate (N=XX)	Stage 2 (N=XX)	Total (N=XX)
Screened positive set - N (%)					
Missing	xxx	xxx	xxx	xxx	xxx
Yes	xx (xx.x%)	xx (xx.x%)	xx (xx.x%)	xx (xx.x%)	xx (xx.x%)
No	xx (xx.x%)	xx (xx.x%)	xx (xx.x%)	xx (xx.x%)	xx (xx.x%)
Total	xxx	xxx	xxx	xxx	xxx
ITT set - N (%)					
Missing	xxx	xxx	xxx	xxx	xxx
Yes	xx (xx.x%)	xx (xx.x%)	xx (xx.x%)	xx (xx.x%)	xx (xx.x%)
No	xx (xx.x%)	xx (xx.x%)	xx (xx.x%)	xx (xx.x%)	xx (xx.x%)
Total	xxx	xxx	xxx	xxx	xxx
mITT set - N (%)					
Missing	xxx	xxx	xxx	xxx	xxx
Yes	xx (xx.x%)	xx (xx.x%)	xx (xx.x%)	xx (xx.x%)	xx (xx.x%)
No	xx (xx.x%)	xx (xx.x%)	xx (xx.x%)	xx (xx.x%)	xx (xx.x%)
Total	xxx	xxx	xxx	xxx	xxx
Evaluable set - N (%)					
Missing	xxx	xxx	xxx	xxx	xxx
Yes	xx (xx.x%)	xx (xx.x%)	xx (xx.x%)	xx (xx.x%)	xx (xx.x%)
No	xx (xx.x%)	xx (xx.x%)	xx (xx.x%)	xx (xx.x%)	xx (xx.x%)
Total	xxx	xxx	xxx	xxx	xxx
PP set - N (%)					
Missing	xxx	xxx	xxx	xxx	xxx
Yes	xx (xx.x%)	xx (xx.x%)	xx (xx.x%)	xx (xx.x%)	xx (xx.x%)
No	xx (xx.x%)	xx (xx.x%)	xx (xx.x%)	xx (xx.x%)	xx (xx.x%)
Total	xxx	xxx	xxx	xxx	xxx

### 9.2.4. Continuous variable

Quantitative variable	Inpatients (N=XX)	Outpatients (N=XX)	Stage 1 or intermediate (N=XX)	Stage 2 (N=XX)	Total (N=XX)
Missing	x	x	x	x	x
N	xx	xx	xx	xx	xx
Mean (±SD)	xx (±xx)	xx (±xx)	xx (±xx)	xx (±xx)	xx (±xx)
Median	xx	xx	xx	xx	xx
Q1-Q3	[xx;xx]	[xx;xx]	[xx;xx]	[xx;xx]	[xx;xx]
Min-Max	[xx;xx]	[xx;xx]	[xx;xx]	[xx;xx]	[xx;xx]

### 9.2.5. Categorical variables

Categorical variable	Inpatients (N=XX)	Outpatients (N=XX)	Stage 1 or intermediate (N=XX)	Stage 2 (N=XX)	Total (N=XX)
Categorical variable - N (%)					
Missing	x	x	x	x	x
Class 1	xx (xx.x%)	xx (xx.x%)	xx (xx.x%)	xx (xx.x%)	xx (xx.x%)
Class 2	xx (xx.x%)	xx (xx.x%)	xx (xx.x%)	xx (xx.x%)	xx (xx.x%)

Class (...)	xx (xx.xx%)				
Total	xx	xx	xx	xx	xx

### 9.2.6. Medical history

System Organ Class / Preferred Term	Inpatients (N=XX)			Outpatients (N=XX)			Stage 1 or intermediate (N=XX)			Stage 2 (N=XX)			Total (N=XX)		
	Nb MH	Nb pat	% pat	Nb MH	Nb pat	% pat	Nb MH	Nb pat	% pat	Nb MH	Nb pat	% pat	Nb MH	Nb pat	% pat
At least 1 MH	xx	xx	xx.X	xx	xx	xx.X	xx	xx	xx.X	xx	xx	xx.X	xx	xx	xx.X
System Organ Class 1	x	x	xx.X	xx	xx	xx.X	xx	xx	xx.X	xx	xx	xx.X	xx	xx	xx.X
– Preferred Term 1	x	x	x.X	x	x	xx.X	x	x	xx.X	x	x	xx.X	x	x	xx.X
– Preferred Term 2	x	x	xx.X	x	x	xx.X	x	x	xx.X	x	x	xx.X	x	x	xx.X
– Preferred Term 3	x	x	x.X	x	x	xx.X	x	x	x.X	x	x	x.X	x	x	x.X
System Organ Class 2	x	x	xx.X	x	x	xx.X	xx	xx	xx.X	xx	xx	xx.X	xx	xx	xx.X
– Preferred Term 1	x	x	x.X	x	x	x.X	x	x	x.X	x	x	x.X	x	x	x.X
– Preferred Term 2	x	x	x.X	x	x	x.X	x	x	x.X	x	x	x.X	x	x	x.X
– Preferred Term 3	x	x	x.X	x	x	x.X	x	x	x.X	x	x	x.X	x	x	x.X

### 9.2.7. Concomitant medication

Therapeutic Class / Preferred name	Inpatients (N=XX)			Outpatients (N=XX)			Stage 1 or intermediate (N=XX)			Stage 2 (N=XX)			Total (N=XX)		
	Nb TRT	Nb pat	% pat	Nb TRT	Nb pat	% pat	Nb TRT	Nb pat	% pat	Nb TRT	Nb pat	% pat	Nb TRT	Nb pat	% pat
At least 1 TRT	xx	xx	xx.X	xx	xx	xx.X	xx	xx	xx.X	xx	xx	xx.X	xx	xx	xx.X
Therapeutic Class 1	x	x	xx.X	xx	xx	xx.X	xx	xx	xx.X	xx	xx	xx.X	xx	xx	xx.X
– Preferred name 1	x	x	x.X	x	x	xx.X	x	x	xx.X	x	x	xx.X	x	x	xx.X
– Preferred name 2	x	x	xx.X	x	x	xx.X	x	x	xx.X	x	x	xx.X	x	x	xx.X
– Preferred name 3	x	x	x.X	x	x	xx.X	x	x	x.X	x	x	x.X	x	x	x.X
Therapeutic Class 2	x	x	xx.X	x	x	xx.X	xx	xx	xx.X	xx	xx	xx.X	xx	xx	xx.X
– Preferred name 1	x	x	x.X	x	x	x.X	x	x	x.X	x	x	x.X	x	x	x.X
– Preferred name 2	x	x	x.X	x	x	x.X	x	x	x.X	x	x	x.X	x	x	x.X
– Preferred name 3	x	x	x.X	x	x	x.X	x	x	x.X	x	x	x.X	x	x	x.X

### 9.2.8. Analysis of the primary endpoint

Description	Statistics	Total (N=XXX)
Success Rate	N	XXX
Missing		x
n (%) – Yes [95CI]	n (XX.X%) [XX.X ; XX.X]	
n (%) – No [95CI]	n (XX.X%) [XX.X ; XX.X]	

### 9.2.9. Overall summary of adverse event

Adverse Event summary	Inpatients (N=XX)	Outpatients (N=XX)	Stage 1 or intermediate (N=XX)	Stage 2 (N=XX)	Total (N=XX)
At least one TEAE - N (%) IC95%					
Yes	xx (xx.x%) [xx.x ; xx.x]	xx (xx.x%) [xx.x ; xx.x]	xx (xx.x%) [xx.x ; xx.x]	xx (xx.x%) [xx.x ; xx.x]	xx (xx.x%) [xx.x ; xx.x]
At least one TEAE leading to treatment discontinuation (temporary or permanent) - N (%) IC95%					
Yes	xx (xx.x%) [xx.x ; xx.x]	xx (xx.x%) [xx.x ; xx.x]	xx (xx.x%) [xx.x ; xx.x]	xx (xx.x%) [xx.x ; xx.x]	xx (xx.x%) [xx.x ; xx.x]
At least one TEAE leading to permanent treatment discontinuation - N (%) IC95%					
Yes	xx (xx.x%) [xx.x ; xx.x]	xx (xx.x%) [xx.x ; xx.x]	xx (xx.x%) [xx.x ; xx.x]	xx (xx.x%) [xx.x ; xx.x]	xx (xx.x%) [xx.x ; xx.x]
(etc.)					
At least one Serious TEAE - N (%) IC95%					
Yes	xx (xx.x%) [xx.x ; xx.x]	xx (xx.x%) [xx.x ; xx.x]	xx (xx.x%) [xx.x ; xx.x]	xx (xx.x%) [xx.x ; xx.x]	xx (xx.x%) [xx.x ; xx.x]
(etc.)					

### 9.2.10. Adverse event by SOC and PT

System Organ Class / Preferred Term	Inpatients (N=XX)			Outpatients (N=XX)			Stage 1 or intermediate (N=XX)			Stage 2 (N=XX)			Total (N=XX)		
	Nb AE	Nb pat	% pat	Nb AE	Nb pat	% pat	Nb AE	Nb pat	% pat	Nb AE	Nb pat	% pat	Nb AE	Nb pat	% pat
At least 1 AE	XX	XX	XX.X	XX	XX	XX.X	XX	XX	XX.X	XX	XX	XX.X	XX	XX	XX.X
System Organ Class 1	X	X	XX.X	XX	XX	XX.X	XX	XX	XX.X	XX	XX	XX.X	XX	XX	XX.X
- Preferred Term 1	X	X	XX.X	X	X	XX.X	X	X	XX.X	X	X	XX.X	X	X	XX.X
- Preferred Term 2	X	X	XX.X	X	X	XX.X	X	X	XX.X	X	X	XX.X	X	X	XX.X
- Preferred Term 3	X	X	XX.X	X	X	XX.X	X	X	XX.X	X	X	XX.X	X	X	XX.X
System Organ Class 2	X	X	XX.X	X	X	XX.X	XX	XX	XX.X	XX	XX	XX.X	XX	XX	XX.X
- Preferred Term 1	X	X	XX.X	X	X	XX.X	X	X	XX.X	X	X	XX.X	X	X	XX.X
- Preferred Term 2	X	X	XX.X	X	X	XX.X	X	X	XX.X	X	X	XX.X	X	X	XX.X
- Preferred Term 3	X	X	XX.X	X	X	XX.X	X	X	XX.X	X	X	XX.X	X	X	XX.X

### 9.2.11. Shift table for laboratory parameters

#### Template by severity:

Parameter XXXX	Laboratory parameter – Visit A			
	Normal	Abnormal NCS	Abnormal CS	Missing
Visit B				
- Normal	X (XX.X%)	XX (XX.X%)	X (XX.X%)	X (XX.X%)
- Abnormal NCS	X (XX.X%)	X (XX.X%)	XX (XX.X%)	XX (XX.X%)
- Abnormal CS	X (XX.X%)	X (XX.X%)	XX (XX.X%)	XX (XX.X%)
- Missing	X (XX.X%)	X (X.X%)	X (XX.X%)	XX (XX.X%)

#### Template by CTCAE grades:

Parameter XXXX	Laboratory parameter – Visit A				
	Grade 1	Grade 2	Grade 3	Grade 4	Grade 5
Visit B					
- Grade 1	X (XX.X%)	X (XX.X%)	XX (XX.X%)	X (XX.X%)	X (XX.X%)
- Grade 2	X (XX.X%)	X (XX.X%)	X (XX.X%)	XX (XX.X%)	XX (XX.X%)
- Grade 3	X (XX.X%)	X (XX.X%)	X (XX.X%)	XX (XX.X%)	XX (XX.X%)
- Grade 4	X (XX.X%)	X (XX.X%)	X (XX.X%)	X (XX.X%)	XX (XX.X%)
- Grade 5	X (XX.X%)	X (XX.X%)	X (X.X%)	X (XX.X%)	XX (XX.X%)

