4.2. Non-inclusion Criteria

To be included in the study, the patient must not fulfil any of the following exclusion criteria:

- Active clinically relevant medical conditions other than HAT that, in the Investigator's opinion, could jeopardise patient safety or interfere with participation in the study, including but not limited to significant liver and cardiovascular diseases, HIV infection, CNS trauma or seizure disorders, coma or altered consciousness not related to HAT;
- Severe renal or hepatic impairment defined as:
 - elevated creatinine at > 3 times the upper limit of normal (ULN);
 - elevated ALT, AST or bilirubin at > 3 X ULN;

Confidential Page 26 of 83

- Severely deteriorated general condition, such as cardiovascular shock, respiratory distress, or terminal illness;
- Any condition (except symptoms of HAT) that compromises ability to communicate with the Investigator as required for completion of the study;
- Any contraindication to imidazole products (known hypersensitivity to imidazoles);
- Treatment for HAT within 2 years prior to inclusion;
- Prior enrolment in the study or prior intake of fexinidazole;
- Foreseeable difficulty in complying with the schedule of follow-up visits (migrants, refugees, itinerant traders, etc.).

The following criteria are considered as temporary non-inclusion criteria:

- Recovery period after antimalarial treatment and/or treatment of helminthiasis (at least 3 days);
- Uncontrolled diabetes or hypertension or any patients requiring clinical stabilisation; wait until appropriate treatment to control the disease has been initiated:
- First trimester of pregnancy (based on date of last menstrual period);
- Traumatic lumbar puncture at Screening i.e. red blood cells visible in CSF; wait for 48 hours before repeating lumbar puncture.

Ineligible patients will be treated according to the protocol of the National HAT Control Program (PNLTHA) and will receive the same support from the Sponsor during the treatment period.

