9.6. Secondary Analyses

9.6.1. Secondary Analysis - Safety

The secondary safety analyses will be performed on the mITT population, i.e. all patients who took at least one tablet of fexinidazole.

The proportion of patients who experienced an SAE and/or an AE leading to treatment discontinuation will be described by system-organ class using Medical Dictionary for Regulatory Affairs (MedDRA) terms and/or NCI CTCAE, version 4.03 (14) and, for certain laboratory parameters, modified CTCAE will be used (see Appendix 6 – CTCAE v4.03 adapted, p 81).

The proportion of patients who experienced at least one AE will be described. Events described using the same term and that occur several times in the same patient will be counted only once. If a patient experiences several events described with the same term, the event with the maximal severity will be included in the analysis. In addition, each SAE will be described in a narrative presenting all aspects of the medical event and the causality assessment.

The incidence of AEs and of SAEs and their respective 95% confidence intervals will be presented by category and by frequency. In other cases, only descriptive statistics will be presented.

Laboratory safety parameters, i.e. haematology and biochemistry, will also be described individually, indicating the proportions of patients by category corresponding to the size of the increase in relation to the ULN for liver function tests (< 1 ULN, 1–2 ULN, 2–3 ULN etc.). Scatter graphs with baseline values on the x-axis and post-treatment values on the y-axis with the bisector indicating the absence of change will be presented. Changes in blood levels over time will be presented in graphs. Shift tables will be provided to supplement signal detection. A listing of patients with clinically significant increases in laboratory parameters will be provided.

Confidential Page 50 of 83

Abnormalities, if any, on ECG tracings recorded on Day 11 will be described.

The proportion of patients hospitalised for a safety problem, including overdose, will also be presented.

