### 6.3.2. Laboratory examination

All laboratory parameters recorded in the CRF in sections “Hematology”, “Biochemistry” and “Urinalysis” will be used. For continuous data, the absolute change from baseline to each timepoints will be derived. In addition, continuous laboratory values will be compared to their reference ranges and classified as “<LLN”, “Normal” and “>ULN” at baseline and each timepoints.

For the following parameters, CTCAE grades will be derived as defined in Appendix 6 of the protocol:

- Hemoglobin
- Platelets
- Leukocytes
- Sodium
- Potassium
- Calcium
- Bicarbonates
- Chloride
- Glucose
- BUN
- Creatinine
- Alkaline phosphatase
- ALAT
- ASAT
- Total bilirubin
- Albumin
- Total protein

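### The CTCAE-grade laboratory shift table has no level for an ungraded value, so it cannot show new-onset graded toxicity or return to normal

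*SAP*

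**What the plan says.** SAP 6.3.2 lists the laboratory parameters for which "CTCAE grades will be derived as defined in Appendix 6 of the protocol". SAP 9.1 then plans, as Table 3.2.1.4, "Shift tables of CTCAE grades between baseline and each time points of haematology parameters". For biochemistry it says "Same outputs as above (except Figure 3.2.1.2"), so the graded shift table is repeated there.

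The layouts are in SAP 9.2.11. The "Template by severity" has four levels on each axis: normal, abnormal not clinically significant, abnormal clinically significant, and missing. The "Template by CTCAE grades" has Grade 1 to Grade 5 as columns (Visit A) and Grade 1 to Grade 5 as rows (Visit B), with no normal, Grade 0 or missing level. Neither layout says which visit is baseline or what the percentages are taken of.

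SAP 8.8.3 describes the clinical-significance shift table but not the graded one. The introduction to SAP 9.2 provides for adapting the templates to the number of groups and mentions no other change. On purpose, protocol 9.6.1 says: "Shift tables will be provided to supplement signal detection".

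**The concern.** A graded shift table is mainly read for patients who start with a normal value and end with a grade, and then for those who recover. This layout has no place for either. It can hold only patients who were already graded at one visit and are still graded at the other.

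The organ systems concerned are the ones the protocol singles out. Section 1.6 says the extra laboratory data are to focus on haematological and hepatic function. Section 1.4 reports liver-function reactions and grade 3 and 4 neutropenia in an earlier study of the drug in Chagas disease. Liver tests and leucocyte count (the nearest graded parameter to neutropenia in Appendix 6) are among those tabulated. A reader looking for a move from normal to Grade 3 would find no cell for it, and could take the absence of a count for the absence of events.

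**Working it through.** The plan states no figure to reproduce. The check is whether each baseline and post-baseline pair has a cell.

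**Inputs.** From protocol Appendix 6, ALT has a ULN of 61 U/L. Grade 1 is above 61 to 183, Grade 2 above 183 to 305, Grade 3 above 305 to 1220, and Grade 4 above 1220. A value of 61 or less has no grade. From protocol 4.2, patients with "elevated ALT, AST or bilirubin at > 3 X ULN" are not included. The axes come from SAP 9.2.11.

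**Example ALT values (U/L), chosen for illustration.**

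| Baseline | Later | Later ÷ 61 | Shift | Cell in template? |
|---|---|---|---|---|
| 40 | 100 | 1.64 | none to Grade 1 | No |
| 40 | 250 | 4.10 | none to Grade 2 | No |
| 40 | 400 | 6.56 | none to Grade 3 | No |
| 40 | 1300 | 21.31 | none to Grade 4 | No |
| 100 | 400 | 6.56 | Grade 1 to Grade 3 | Yes |
| 100 | 40 | 0.66 | Grade 1 to none | No |

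**Cell count.** The template has 5 × 5 = 25 cells. With an ungraded level on both axes it would have 6 × 6 = 36. The 36 − 25 = 11 absent cells are 5 for new onset, 5 for return to normal, and 1 for normal at both visits.

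**Effect of eligibility.** The inclusion limit for ALT is 3 × 61 = 183 U/L, which is the top of Grade 1. A patient who meets the criterion is therefore ungraded or Grade 1 at baseline, and the same holds for AST (3 × 60 = 180). For these two tests only one of the five baseline levels in the template can be filled, and patients with a normal baseline drop out.

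**Grade 5.** Where Appendix 6 defines Grade 5 for a laboratory parameter, it is death. The 5 cells with Grade 5 at baseline can therefore never be filled. Grade 5 after baseline is defined for anaemia, leukocytosis, sodium, potassium, glucose, calcium and albumin.

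**Parameters without numeric grades.** SAP 6.3.2 includes bicarbonates, chloride, BUN and total protein among those to be graded. For these, Appendix 6 gives only a judgement of normal, abnormal not clinically significant, or abnormal clinically significant. Those are the levels of the severity template.

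**The case against.** The strongest reply is that the report as a whole does not hide new-onset abnormality. A reader might infer from the template that such toxicity is shown nowhere, and the documents do not support that.

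- SAP 8.8.3 requires scattergrams of baseline against each timepoint for every laboratory parameter. These plot patients with a normal baseline and do not depend on the investigator's judgement.
- The clinical-significance shift table has a normal level.
- ALT, AST, bilirubin and alkaline phosphatase are tabulated by multiple of ULN.
- Abnormalities that investigators report as AEs enter the AE tables.
- Individual haematology and biochemistry values are listed.

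This stands, and it limits the point to one table. Each of these displays still lacks something. The scattergrams give no counts by grade. The severity table uses the significance call and not the grade. The ULN categories cover four liver tests and are not crossed with baseline. The AE tables hold only what was reported as an AE. The listings are not a summary.

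A second reply is that the templates are shells and not rules. SAP 9.2 says they are designed for four groups, yet several show five columns, and no text tells the programmer to exclude ungraded patients. That is fair, and a programmer might add the level unprompted. But no text supplies it either, and the template is the only specification of this table.

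A third reply is that protocol 9.6.1 asks for shift tables without asking for graded ones, so the severity table meets it. This also stands: the fault lies in an output that the SAP added, and it is not a breach of the protocol.

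It is also tempting to put a head count on the loss by applying an assumed share of normal baselines to the planned 174 patients. The documents give no such share. Nor is 174 the number with paired values at every visit, since protocol 6.7.2 calls for laboratory tests at 12 and 18 months only if clinically indicated.

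**Conclusion.** The point holds for the CTCAE-grade shift tables in haematology and biochemistry. As laid out, they cannot show new-onset graded toxicity, return to normal, or missing values, and no other planned display cross-tabulates a normal baseline against the post-baseline CTCAE grade. The size is structural: 11 of the 36 cells of a complete graded table are absent, among them every new-onset cell. For ALT and AST, eligible patients can fill only one baseline level. The number of patients affected cannot be stated from the documents.

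The conclusion assumes that the tables are programmed as the template shows. It concerns the display of safety data only. No estimate, analysis set or efficacy result changes, so this is a minor point that is worth correcting because the correction is so cheap.

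**What to change.** Edit the CTCAE template in SAP 9.2.11 as follows.

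- Add Grade 0/Normal and Missing to both axes, as the severity template already does. Define the first as no grade assigned, because Appendix 6 also leaves some out-of-range values ungraded (leucocytes above 9,100 and up to 100,000 per µL, for example).
- Label Visit A as baseline and Visit B as the post-baseline visit.
- Use patients with a baseline value as the percentage denominator at each visit, and count patients with a missing baseline separately.
- Remove Grade 5 from the baseline axis only. A reader might want it dropped altogether, but Appendix 6 lists it as death for several parameters and SAP 6.3.2 follows Appendix 6, so it should stay on the post-baseline axis.
- For bicarbonates, chloride, BUN and total protein, use the severity template.
- Add a sentence to SAP 8.8.3 describing the graded shift table.

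The result has 6 baseline levels (Grades 0 to 4 and Missing) by 7 post-baseline levels (Grades 0 to 5 and Missing), or 42 cells. The cost is a template edit and a small programming change, with no new data. SAP Section 11 already records a change made after database lock, so this edit should be dated and recorded there too.
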